# 2.2 Assessment and management of risk

The British National Formulary lists the common or very common side effects of acetazolamide to be: ataxia, depression, diarrhoea, dizziness, fatigue, flushing, irritability, headache, loss of appetite, nausea, vomiting, taste disturbance, parasthesiae, reduced libido, polyuria, and thirst. Notable uncommon side effects include: metabolic acidosis, electrolyte disturbances, blood disorders, skin rashes and symptoms consistent with renal calculi.

The early studies suggested that side effects such as drowsiness and paraesthesia are seen in 14-38% of patients with heart failure at doses >1000mg per day, although side-effects were less common at doses ≤500mg per day (5-10%). Modern day studies did not report any adverse events but it is not explicitly stated that this is due to the medication being well tolerated.

We judge the above side effects to be of low clinical risk to the patient however it is possible a patient experiencing any one of the those side effects after starting acetazolamide may wish to end their participation. This, in itself, would be a useful endpoint. One of the many unknowns about acetazolamide in contemporaneous studies is the tolerability used either in isolation or in conjunction with high dose loop diuretic.

There are potential risks to the patient from the combination of acetazolamide and high-dose loop diuretic treatment, however we are unable to estimate their expected frequency: 1) increased risk of hyponatraemia – as both medications increase urinary sodium excretion; 2) increased risk of symptomatic hypotension due to increased intravascular volume loss and 3) increased risk of renal dysfunction. Daily assessment of urine and serum electrolytes and the patient will detect any changes that might be associated with increased risk to the patient and these will be discussed with the patient regarding continuation. Again, this would be a useful endpoint in itself regarding tolerability of the combination of diuretics. Furthermore, worsening electrolyte abnormalities, symptomatic hypotension and worsening renal function would be expected in the standard care arm also.

Ultimately we would expect all treatment related adverse events to resolve upon withdrawal of the study treatment should the patient wish to do so or if the risk to the patient was felt too great to allow their continuation in the study.

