# 7.7 Schedule of Events

		Visits							
Procedures	On Admission	Visit 1 Screening	Visit 2 Baseline (Day 1 – 0hrs)	Visit 3 Day 2 – 24hrs	Visit 4 Day 3 - 48hrs	Visit 5 Day 4 – 72hrs	Visit 6 Day 5 – 96hrs	Visit 7 30 Day Follow Up	Visit 8 180 Day Follow Up
Informed consent		Х							
Demographics		Х							
Medical history	X (RC)	Х							
Physical examination	X (RC)	Х	Х	Х	Х	Х	х		
Vital signs									
Height			Х						
Weight*			Х	Х	Х	Х	Х		
BMI			Х						
BP			Х	Х	Х	Х			
HR			Х	Х	Х	Х			
Concomitant medications		Х							
Ward round assessments by treating teams **	Х	Х	х	х	х	х	х		
ECG	X (RC)	Х							
Chest X-ray	X (RC)								
Laboratory tests									
FBC	X (RC)		Х	Х	Х	Х			
Urea & Electrolytes	X (RC)		Х	Х	Х	Х			

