# Visit 2 - Day 1 – 0 hours

Visit 2 can occur on the same day as screening if randomisation occurs before 12PM and the first dose of acetazolamide is given before 12PM (ACZ arm only).

- Furosemide infusion to continue
- Vital signs measured by nursing staff
- Bloods taken
  - o Urea and electrolytes
  - Full blood count
- Acetazolamide 250mg to be given by ward staff in the morning and again 6 hours later as prescribed on the electronic prescription (in ACZ group only)
- Ongoing input from treating team: ward round and any input that stems from that, regular observations from nursing staff, input from other health professionals if indicated (for example dieticians, physiotherapists, occupational therapists)
- Study doctor visit at +/- 2 hours from first dose of acetazolamide / randomisation (SoC arm)
   Clinical examination

- NTproBNP added to blood tests taken in the morning if not performed on admission
- Weight measured using the same set of scales
- Ultrasound assessment of congestion
  - Inferior vena cava diameter
- Patient assessed breathlessness using 5-point Likert breathlessness scale
- Diet sheet to be completed at 1800 (after evening meal)
- Patient provided with 24hr urine electrolyte bottle if not catheterised and instructed to begin collection at 24hrs from the first dose of acetazolamide the following day
  - Nursing staff to be informed

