#### 7.9 Withdrawal criteria

Patients can be withdrawn from the trial if:

- They withdraw their consent at any point during the study **for any reason**. This can happen at any time after consent and during follow up. In such an event no additional data will be collected from the patient and there will be no follow up. The study doctor will ascertain whether the patient wishes the withdrawal of consent to apply retrospectively to the withdrawal (i.e. can we use data already collected?). The outcome of any and all discussions regarding the withdrawal of consent will be documented in the medical notes and case report form.
- A patient's condition deteriorates due to heart failure or another pathology to the extent that they are expected to die within the next 24 to 48 hours.
- The study doctors deems the risk of continuation due to serious drug reactions or adverse events is too great to the patient. This will be fully discussed with the patient and the content and outcome of all discussions will be documented in the medical notes and CRF.
  - Worsening symptoms of heart failure\*
  - Hyponatraemia (<135 mmol/L)
    - Asymptomatic\*
      - Severe (<130 mmol/L)\*

    - Symptomatic (confusion, drowsiness, nausea or vomiting)\*\*
  - Hypotension
    - Asymptomatic\*
    - Symptomatic with no sequelae\*
    - Symptomatic with significant sequelae i.e. fall due to postural hypotension\*\*
  - o Hyperchloraemia
    - Mild 107 110 mmol/L\*
    - Severe >110mmol/L\*\*
  - Worsening renal function
    - >30% increase in serum creatinine from admission. \*
    - >50% increase in serum creatinine from admission.\*
    - >100% increase in serum creatinine from admission.\*\*
  - Side effects of acetazolamide: haemorrhage, ataxia, depression, diarrhoea, dizziness, fatigue, flushing, irritability, headache, loss of appetite, nausea, vomiting, taste disturbance, paraesthesia,
    - Tolerable to the patient.\*
    - Intolerable to the patient.\*\*

\* - Clinically relevant safety endpoint that would not automatically lead to the discontinuation of the study drug. Withdrawal would be at patient's request or the study doctor's discretion if the risk of continuation was deemed too high.

\*\* - Occurrence would lead to withdrawal from the study if it occurred in the acetazolamide arm

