# 9.2 Operational definitions for (S)AEs

Due to the pilot and exploratory nature of this study **all** adverse events and adverse reactions will be recorded. All serious adverse events serious adverse reactions, and suspected unexpected serious adverse reactions will be reported.. This will enable collection on safety data for the use of ACZ concurrently with high dose loop diuretics as well as data on the tolerability of treatment for a future trial.

	Asymptomatic hypotension (systolic blood pressure (SBP) <90 mmHg)
	Symptomatic hypotension (SBP <90 mmHg and symptoms of: dizziness or presyncope)
	Asymptomatic hyponatraemia (serum sodium concentrations <130 mmol/L)
Adverse Events	Symptomatic hyponatraemia (serum sodium concentrations <130 mmol/L and symptoms of fatigue, nausea, vomiting, or headache not promoting further treatment or investigation)†
	Flare of gout requiring oral treatment and analgesia
	Decrease in estimated glomerular filtration rate >50% of baseline value
	† Treatment of headache with analgesia not included in this definition however treatment of nausea or vomiting with antiemetic is.
	Symptomatic hypotension with sequelae (SBP <90 mmHg and symptoms of: dizziness or presyncope and fall or injury as a direct result)
	Symptomatic hyponatraemia with sequelae (serum sodium concentrations <130 mmol/L and symptoms of fatigue, nausea, vomiting, headache which prompt further treatment or investigation,† or confusion or seizure deemed secondary to hyponatraemia).
	Decrease in eGFR >100% of baseline value or serum creatinine >221µmol/L
	Deterioration in condition during trial defined as:
Serious Adverse Events	
 
Deemed to need escalating doses of loop diuretic or the addition of a second diuretic agent such as thiazide diuretic.
 
Deemed to need inotropic support
 
New diagnosis of infection
 
New diagnosis of another concurrent illness that will prolong hospital stay
 
Transition to end-of-life care
 
Death
 

	Overdose of ACZ or furosemide infusion defined as 1) >500mg given per day of ACZ or 2) >240mg IV furosemide per day.
Adverse Reactions	Metabolic acidosis bicarbonate <23 mmol/L
	Hyperchloraemia 107-110 mmol/L

	Teaching Hospi	tals
	Any of the following possible side effects of acetazolamide that are NHS tolerable to the patient: haemorrhage, ataxia, depression, diarrhoea,	Trust

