# 10.3.3 Secondary outcome analysis

Secondary outcomes are exploratory and none are powered for statistical significance. Secondary outcomes that are measured as continuous variables (difference in daily urine output; difference in weight from baseline to day 4; difference in change in serum sodium potassium, bicarbonate, urea, creatinine, and estimated glomerular filtration rate between baseline and day 4; urinary electrolyte concentrations at day 2 and day 4; inferior vena cava diameter; change in breathlessness score (Likert scale); time to clinical euvolaemia; and length of stay) will be assessed using independent samples t-test, and unadjusted linear regression (with treatment assignment as the independent variable), and linear regression adjusted for daily salt intake and median number of hours of furosemide per day.

Secondary outcomes that are measured as categorical variables (incidence of hyponatraemia, hypochloraemia, hypokalaemia, metabolic alkalosis (serum bicarbonate concentrations >29 mmol/L) or metabolic alkalosis (serum bicarbonate concentrations <23 mmol/L); clinical assessment of congestion; proportion of patients with IVC diameter >2cm; proportion of patients with JVD ratio <4; rate of adverse and serious adverse events; rate of drop-out after randomisation will be assessed using chi-squared tests, un-adjusted logistic regression (with treatment assignment as the independent variable), and logistic regression adjusted for daily salt intake and median number of hours of furosemide per day.

Survival analysis (time to cause specific hospitalisation and time to cause specific mortality) will be conducted with a time-to-first event analysis using Kaplan-Meier and logrank tests, un-adjusted Cox proportional-hazard outcome models.

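### The mandatory renal stop in section 7.9 is measured only from admission creatinine, so a doubling on acetazolamide after a fall before Day 1 need not trigger it

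*Protocol*

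**What the plan says.** Section 7.9 lists three levels of worsening renal function (rises above 30%, 50% and 100%), all measured from the admission creatinine. The two lower levels, starting with ">30% increase in serum creatinine from admission", carry a single asterisk, explained as "Clinically relevant safety endpoint that would not automatically lead to the discontinuation of the study drug". Withdrawal at those levels is left to the patient or the study doctor. The top level, ">100% increase in serum creatinine from admission", carries a double asterisk and leads to withdrawal if it occurs in the acetazolamide arm. It is the only renal criterion in the protocol that does so.

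Elsewhere the reference is baseline. The renal adverse event in 9.2 is "Decrease in estimated glomerular filtration rate >50% of baseline value", and section 10.3.3 compares the arms on change in "creatinine, and estimated glomerular filtration rate between baseline and day 4".

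Both reference values will exist. In the section 7.7 schedule the "Urea & Electrolytes" row is marked on admission (routine care), at Visit 2 (baseline, Day 1) and at Visits 3 to 5.

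**The concern.** Section 2.2 names "increased risk of renal dysfunction" among the potential risks of adding acetazolamide to high-dose furosemide. A mandatory stop that applies only in the acetazolamide arm should respond to what happens on acetazolamide. An admission reference mixes in whatever happened before the first dose.

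The interval before the first dose is not fixed. Section 5 says most patients are admitted first at another hospital. Section 7.8 has intravenous furosemide started on admission and possibly changed later. Section 7.1.2 allows up to three re-screens at 48-hour intervals (3 × 48 = 144 hours), although Visit 2 may also fall on the screening day. Eligibility sets an absolute eGFR limit but no limit on change since admission. A patient who first failed on eGFR could therefore enter because creatinine had fallen. The risk table in Appendix 1 itself recognises that renal function can improve during an admission.

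If creatinine has fallen by Day 1, the stop sits above twice the patient's own pre-treatment value. The same on-trial injury would then be a compulsory withdrawal in one patient and a matter of discretion in another.

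**Working it through.** The plan gives no figure to reproduce. The check is direct arithmetic on the wording of 7.9. All creatinine values below are illustrative (µmol/L).

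**Definitions.** A = admission creatinine, D = Day 1 creatinine, P = an on-trial value, r = D/A.

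**When the stop fires.** It needs P > 2A. Dividing by D, it needs P/D > 2/r, so the on-trial rise must exceed 2/r − 1. A bare on-trial doubling (P = 2D) appears from admission as a rise of 2r − 1.

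| r | On-trial rise needed (2/r − 1) | A doubling since Day 1, seen from admission (2r − 1) |
|---|---|---|
| 1.00 | +100% | +100% |
| 0.90 | +122% | +80% |
| 0.80 | +150% | +60% |
| 0.67 (2/3) | +200% | +33% |

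**Two examples (admission, Day 1, peak).**
- 120, 100, 205: on trial 205/100 = 2.05 (+105%); from admission 205/120 = 1.71 (+71%). The stop needs more than 2 × 120 = 240 and does not fire.
- 150, 100, 205: on trial again +105%; from admission 205/150 = 1.37 (+37%). The stop needs more than 2 × 150 = 300 and does not fire.

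**What else catches these patients.**
- *Discretionary levels in 7.9.* The first example passes the 30% and 50% levels, the second the 30% level. A bare doubling passes 30% whenever 2r − 1 > 0.30, that is r > 0.65. Below that it meets no renal level in 7.9: at r = 0.60 it reads +20%.
- *Adverse event in 9.2.* Taking eGFR as inversely proportional to creatinine (Cockcroft-Gault with age and weight fixed), the fall from baseline is 1 − D/P, here 1 − 100/205 = 51%. Any rise above a doubling since Day 1 gives a fall above 50%, so the adverse event is met.
- *Serious adverse event in 9.2.* Its creatinine limit is above 221 µmol/L, which 205 does not reach. With Day 1 at 100, an on-trial doubling lies above 200. With admission at 120, values above 200 and up to 221 have neither the stop nor this serious event, and values above 221 and up to 240 have the serious event but no stop. With admission at 150 the second band runs up to 300. If Day 1 creatinine is above 221/2 = 110.5, every on-trial doubling exceeds 221.

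Neither 9.2 event is tied to withdrawal.

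**The opposite direction.** For 100, 150, 201 the rise from admission is +101% and the on-trial rise is 201/150 − 1 = +34%. Here the admission reference makes the stop fire early, which is protective.

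**How much treatment is at stake.** Eight tablets are given over four days, two per day. After Day 1, urea and electrolytes are scheduled on Days 2, 3 and 4. A stop on the Day 2 sample could spare at most 8 − 2 = 6 tablets, and one on the Day 4 sample at most 2.

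**The case against.** A bedside stopping rule may reasonably use admission as its reference while adverse event definitions and analyses use baseline; nothing in the protocol requires them to match. After a rise before Day 1, admission is the more cautious reference. The gap needs a particular course: a fall before Day 1, then more than a doubling within the sampled 72 hours. The protocol gives no evidence that any of its 40 to 50 patients would follow it. Patients are also seen daily by a study doctor, who can withdraw them, and a serious adverse event goes to the sponsor within 24 hours.

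All of this stands. It limits the point to a small one and is a good reason to keep the admission stop. It does not close the gap, because discretion and event reporting are not the compulsory withdrawal that 7.9 chose for a doubling.

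A reader might also infer that a rise before randomisation contaminates a reported safety endpoint. For example, 100, 140, 140 reads +40% from admission with no on-trial change, and the footnote in 7.9 does use the word endpoint. The documents do not support that inference. The single-asterisk levels are prompts for discretionary withdrawal, and no outcome in 3.5 and no analysis in 10.3.3 uses them. The renal outcome covers the treatment period, and the 9.2 renal events are relative to baseline or an absolute limit. The only link to a listed outcome would be a discretionary withdrawal counted in the drop-out rate. At most this is a note on labelling.

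**Conclusion.** The point holds as a minor gap in one stopping rule. Whenever creatinine is lower on Day 1 than on admission, there is a range of more-than-doublings on acetazolamide that does not trigger the mandatory stop. The range widens with the size of the fall: the on-trial rise needed is +122% after a 10% fall and +150% after a 20% fall. The algebra follows from the wording of 7.9 alone. The r values and creatinine figures are assumptions, and how often the situation would arise cannot be estimated from the protocol.

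Two stronger readings should be avoided. These patients would not go unnoticed, since the baseline-referenced adverse event applies to any on-trial rise above a doubling (with eGFR taken as above). Nor is the comparison of renal function between the arms affected, since it runs from baseline to day 4. The change is worth making because it is cheap, not because the trial's conclusions depend on it.

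**What to change.** In section 7.9, keep the mandatory line ">100% increase in serum creatinine from admission" and add after it: *or from Day 1 (Visit 2, sample drawn before the first acetazolamide dose)*. The two discretionary levels can stay as they are. If the sponsor wishes, a short note can say that rises measured from admission are clinical prompts and are not reported as on-trial events.

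The timing words are needed because Visit 2 in section 7.8 lists the bloods and the morning dose without giving their order. Its line "NTproBNP added to blood tests taken in the morning if not performed on admission" places the bloods in the morning, but not before the dose.

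The cost is wording only, since Day 1 urea and electrolytes are already scheduled in both arms. The downside is that the stop may fire slightly more often in the acetazolamide arm. Section 7.9 already provides for trying to replace patients who withdraw before completing the Day 4 assessments.

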# 7.10 Storage and analysis of samples

All blood and urine samples will be collected as per protocols developed by the Pathology Laboratories at Hull University Teaching Hospitals Trust, tested in the Castle Hill Hospital or Hull Royal Infirmary laboratories and destroyed thereafter in accordance with local protocols.

As all serum sampling for the trial will be done as part of routine care, venepuncture can be performed by any member of the medical, nursing or study team as long as they are trained and competent to do so. The volume of blood and type of tubes used for the full blood count, biochemical profile and NTproBNP will be as per local protocols. All blood tests will be sent to the lab and processed there the same day as per local protocols. Results will be published on the patient's electronic record when available and data entered into the CRF from there. The 24 hour urine collections that lie outside of the tests performed as part of routine care will be collected by nursing staff and/or the study doctor on the wards the samples will be sent to the local laboratory the same day as per local protocol.

Destruction of all samples will occur after analysis as per local protocols whether collected as part of routine care (blood samples) or part of the study (24 hour urine samples). Destruction of the study specific urine samples will be recorded by the local laboratory.

It is the responsibility of the Principle Investigator and Research Team to ensure that samples are appropriately labelled in accordance with the trial procedures to comply with the 1998 Data Protection Act. Biological samples collected from participants as part of this trial will be transported, stored, accessed and processed in accordance with national legislation relating to the use and storage of human tissue for research purposes and such activities shall at least meet the requirements as set out in the 2004 Human Tissue Act and the 2006 Human Tissue (Scotland) Act.

# 7.11 End of trial

An end of trial declaration form will be submitted to the MHRA, REC and HUTH R&D **within 90 days** from completion of the trial and **within 15 days** if the trial is discontinued prematurely. A summary of the trial final report/publication will be submitted to the MHRA, REC and HUTH R&D **within 1 year** of the end of trial. HUTH R&D will be notified immediately of any reason to halt the trial. The Principal investigator and HUTH R&D as sponsor will decide if the trial should be halted temporarily. The MHRA, REC and HUTH R&D will be notified **within 15 days** of a decision to temporarily halt the trial by submitting a substantial amendment notification.

# 8 TRIAL MEDICATION

Medicinal product	Route of administration	Dose	Regulatory status	Storage
Acetazolamide	By mouth (oral)	250mg	Approved for treatment of: Glaucoma: Abnormal retention of fluids. Epilepsy	Manufacturer advises to do not store above 25°C.

Acetazolamide – 250mg tablets, immediate release.

# Furosemide – 10mg / ml, solution for injection

Medicinal product	Route of administration	Dose	Regulatory status	Storage
Furosemide	Intravenous	10mg/ml	Approved for treatment of: Oedema and/or ascites caused by cardiac or hepatic diseases Oedema caused by renal diseases Pulmonary oedema Hypertensive crisis	Do not store above 25°C. Do not refrigerate. Keep the ampoules in the outer carton in order to protect from light.

# 8.1 Missed Doses

If dose is missed, the missed dose should be taken as soon as remembered. However, if this is within two hours of the next dose then skip the missed tablet and carry on taking the rest of the tablets as usual. Do not take a double dose to make up for a forgotten dose. Following this patients can then resume their regular dosing schedule. If intravenous access is lost at any time during the study period the patient will not have been receiving the active comparator (IV furosemide). We will record the amount of time without IV furosemide in the CRF and if a patient has >6 hours without receiving IV furosemide we will attempt to replace the patient data.

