# 8.5 Dosage schedules

The acetazolamide will be taken orally as it has good oral bioavailability (70-90%) reaching peak concentrations after 2 hours with a plasma half life of 4 hours. All other adjunctive diuretics are routinely given orally in the UK – e.g. Bendroflumethiazide, metolazone, dapagliflozin, empagliflozin.

ACZ will be given in the morning and again 6 hours later so that the maximal diuretic effect occurs in the daytime to reduce the chance of the patient waking in the night. The maximum daily dose is 500mg in maximum split doses of 250mg. There will be no individualised dosing. Duration of treatment is 4 days. Furosemide infusions will be continuous as long as is clinically indicated and replenished as and when required.

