# Serum chloride concentrations

Low serum chloride is associated with adverse outcome in patients with HF. We estimate a clinically meaningful change in chloride to be -0.9 mmol/L per day over the course of an admission (9 days) and -3.6 mmol/L over the four day period of our study (appendix 7). To detect such a difference with 80% power and 5% two-tailed significant with the above anticipated drop out rate we would need to recruit a minimum of 14 patients in the control arm and 17 patients in the ACZ arm.

We expect two potential confounding factors for the co-primary endpoints: 1) daily salt intake and 2) loss of IV access reducing the amount of IV furosemide given. We will collect data on both potential confounders using a daily dietary sheet (on which the patient will record their meals for the day and from which the daily salt intake will be estimated) and recording the "number of hours of furosemide" per day. We do not expect any patient to have excessive salt intake (defined by the European Society of Cardiology Heart Failure Guidelines 2021 as >5g per day). Any patient with >5g salt intake per day or <20 hours of furosemide per day will be removed from the analysis. Due to the exploratory nature of the study we will conduct an intention to treat analysis and a per-protocol analysis in which only patients who completed the study without deviating from the protocol will be included. Thus, we will recruit a maximum of 50 patients – 23 in the control arm and 27 in the ACZ arm with anticipated drop out of 10% and 20% respectively. The extra patients recruited will also act as a contingency should any patient need to be removed from the analyses for reasons of excess salt intake, prolonged loss of IV access, or for the per-protocol analysis.

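### The furosemide-gap limit for replacing a patient (8.1) differs from the limit for removing one (10.1, 10.3.2), and the acetazolamide catch-up rule is not tied to a defined daily maximum

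*Protocol*

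**What the plan says.** **Furosemide.** Section 8.5 describes the treatment as uninterrupted: "Furosemide infusions will be continuous as long as is clinically indicated". For loss of intravenous access, section 8.1 says the time off infusion goes in the CRF and that "if a patient has >6 hours without receiving IV furosemide we will attempt to replace the patient data". It does not say whether the six hours are one gap, a daily total or a total over the four days.

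Section 10.1 (under serum chloride concentrations) names loss of access as one of two expected confounders of the co-primary endpoints and states: "Any patient with >5g salt intake per day or <20 hours of furosemide per day will be removed from the analysis". Section 10.3.2 repeats the rule. Section 10.1 adds that the extra patients, up to the maximum of 50, are a reserve for removals, prolonged loss of access included.

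**Acetazolamide.** Section 8.5 schedules a morning tablet and a second one six hours later, and says: "The maximum daily dose is 500mg in maximum split doses of 250mg". Section 8.1 says of a missed tablet that "the missed dose should be taken as soon as remembered", with one limit on timing: "if this is within two hours of the next dose then skip the missed tablet". Section 9.2 lists ">500mg given per day of ACZ" as an overdose under serious adverse events. Section 9.9 removes a patient with an overdose from the analysis and replaces them. None of these sections says what a day is for this purpose.

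**The concern.** The two furosemide rules address the same event but use different limits, and only one has a period. Replacement appears meant to make good the patients lost to analysis, since 10.1 provides spare recruits for that reason. With unmatched triggers, some removed patients are not replaced under 8.1, and some patients who stay in the analysis may be replaced. In a trial of 40 to 50 patients each such case matters a little: one patient is 1/40 = 2.5% of the target. The trial is also open label, so a rule that can be read in several ways leaves room for judgement after the allocation is known.

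For acetazolamide, ward staff could follow 8.1 exactly and, depending on how a day is counted, produce an event that 9.2 classes as an overdose and 9.9 turns into removal and replacement.

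**Working it through.** No power or sample-size figure is involved. The check sets the rules side by side and applies them to simple cases.

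**Furosemide**

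Inputs: continuous infusion, so 24 h is a full day (8.5); removal below 20 h per day (10.1, 10.3.2); replacement attempted above 6 h without infusion, no period (8.1); four treatment days.

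Gap implied by section 10: 24 − 20 = 4 h. A patient is removed if any day has a gap above 4 h.

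| Gap pattern over 4 days | Total gap | Lowest daily hours | Removed (section 10) | Replaced (8.1, single gap) | Replaced (8.1, cumulative) |
|---|---|---|---|---|---|
| 4 h once | 4 h | 20 | No | No | No |
| 5 h once | 5 h | 19 | Yes | No | No |
| 6 h once | 6 h | 18 | Yes | No | No |
| 7 h once | 7 h | 17 | Yes | Yes | Yes |
| 3.5 h on each of 2 days | 7 h | 20.5 | No | No | Yes |
| 2 h on each of 4 days | 8 h | 22 | No | No | Yes |

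The 5 h and 6 h rows show removal without replacement on either reading of 8.1. The last two rows show replacement without removal, conditional on the cumulative reading.

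**Acetazolamide**

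Inputs: 250 mg per tablet; second tablet 6 h after the first; catch-up allowed until 2 h before the next tablet; maximum 500 mg. The clock time of the morning dose is an assumption, taken as 08:00.

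After the second dose falls due at 14:00, the next tablet is 24 − 6 = 18 h away, at 08:00. A missed second dose may therefore be taken under 8.1 at any time up to 06:00 the next day.

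- *Calendar day.* A catch-up between 00:00 and 06:00, then 08:00 and 14:00 as scheduled: 3 × 250 = 750 mg on that date. A catch-up before midnight leaves 500 mg on each date.
- *Rolling 24 h.* A second dose taken at any time after 14:00 falls less than 24 h before the 14:00 tablet next day, with the 08:00 tablet between them: 3 × 250 = 750 mg.
- *Days counted from the first dose.* Day 1 runs from 08:00 to 08:00. A catch-up up to 06:00 is at most 22 h after the first dose and belongs to Day 1. Day 1 = 2 × 250 = 500 mg and Day 2 = 500 mg, so there is no breach.

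Moving the assumed morning dose between 07:00 and 12:00 shifts the clock times but gives the same 750 mg on the first two counts. The instruction in 8.1 against doubling a dose does not prevent this, because the three tablets are taken at separate times. The supply of eight tablets is not exceeded.

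**The case against.** **Different actions may have different limits.** Section 8.1 triggers replacement and section 10 triggers removal. A reader might infer that the number analysed depends on which section is applied. The documents do not support that: 8.1 removes nobody, and the furosemide removal rule has the same limit in 10.1 and 10.3.2. What stands is narrower. The protocol gives no reason for the difference, and the triggers do not match although the actions are linked.

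**The reserve in 10.1 covers removed patients.** It does so in part. It supplies spare numbers but does not say when a replacement is due, so it softens the mismatch without reconciling it.

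**Hours are a poor measure of exposure.** A reader might object that an infusion run for 24 h at half rate would pass. That does not fit the protocol: eligibility requires 10 mg/hr, and section 7.8 treats a patient whose diuretic is de-escalated as having completed the study early. Hours at a fixed rate are a reasonable measure of lost access.

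**The acetazolamide breach depends on how a day is defined.** This stands. The visit schedule in 7.7 and 7.8 runs in 24-hour steps from the first dose, and on that count the total stays at 500 mg. The calendar-day case also needs a tablet given after midnight, which would be uncommon because 8.3 has tablets offered at the morning and afternoon drug rounds. A reader might infer a plain 50% excess over the maximum, but the documents support 750 mg only under a calendar-day or rolling count. Nor does a late tablet contradict the preference for daytime effect in 8.5, which is a rationale rather than a rule. It remains true that 8.5 and 9.2 do not define the day, and that 8.1 does not refer to the maximum.

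**Conclusion.** The point holds in two parts of unequal strength.

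1. The furosemide mismatch follows directly from the text: more than 4 h in a day for removal, more than 6 h with no period for replacement. Every single gap above 4 and up to 6 h in a day leads to removal without triggering replacement. The reverse case, 8 h lost as four gaps of 2 h, rests on reading the six hours as cumulative. How many patients would be affected is unknown, since the protocol gives no rate for loss of access.

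2. The acetazolamide conflict is conditional. On a calendar-day count (with a catch-up after midnight) or a rolling 24-hour count, following 8.1 after a missed second dose can give 750 mg against 500 mg, which 9.2 and 9.9 treat as an overdose with removal and replacement. On days counted from the first dose there is no conflict.

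Neither part undermines the design. Both affect who is replaced, removed or reported, and both can be settled by wording.

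**What to change.** - State one furosemide-interruption criterion, in hours and with one stated period, and use it unchanged in 8.1, 10.1 and 10.3.2, so that replacement and any removal from an analysis set follow the same trigger.
- Define *per day* for the acetazolamide maximum in 8.5 and the overdose definition in 9.2 (calendar day, rolling 24 h, or 24 h from the first dose).
- Reconcile the catch-up rule in 8.1 with 8.5, 9.2 and 9.9 under that definition. Which limit and which dosing rule apply is for the investigators to decide.

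The cost is wording in these sections. No new data are needed: time without furosemide already goes in the CRF (8.1), hours of furosemide per day are already planned (10.1), and the taking of medicines is already in the electronic record (8.10).
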